## Definition of Adverse Events

An **Adverse Event (AE)** is defined as any new untoward medical occurrence or worsening of a preexisting medical condition in a clinical investigation subject administered an investigational product and that does not necessarily have a causal relationship with this treatment. An AE can therefore be any unfavorable and unintended sign (such as an abnormal laboratory finding), symptom, or disease temporally associated with the use of investigational product, whether considered related to the investigational product.

The causal relationship to study drug is determined by a physician and should be used to assess all adverse events (AE). The causal relationship can be one of the following:

Related: There is a reasonable causal relationship between study drug administration and the AE.

Not related: There is not a reasonable causal relationship between study drug administration and the AE.

The term "reasonable causal relationship" means there is evidence to suggest a causal relationship.

Adverse events can be spontaneously reported or elicited during open-ended questioning, examination, or evaluation of a subject. (To prevent reporting bias, subjects should not be questioned regarding the specific occurrence of one or more AEs.)

**Serious Adverse Events.** A Serious Adverse Event (SAE) is any untoward medical occurrence that at any dose:

- Results in death
- Is life-threatening (defined as an event in which the subject was at risk of death at the time of the event; it does not refer to an event which hypothetically might have caused death if it were more severe)
- Requires inpatient hospitalization or causes prolongation of existing hospitalization (see **NOTE** below)
- Results in persistent or significant disability/incapacity
- Is a congenital anomaly/birth defect?
- is an important medical event (defined as a medical event(s) that may not be immediately life-threatening or result in death or hospitalization but, based upon appropriate medical and scientific judgment, may jeopardize the subject or may require intervention [e.g. medical, surgical] to prevent one of the other serious outcomes listed in the definition above.) Examples of such events include, but are not limited to, intensive treatment in an emergency room or at home for allergic bronchospasm; blood dyscrasias or convulsions that do not result in hospitalization.) Potential drug induced liver injury is also considered an important medical event.
- Suspected transmission of an infectious agent (e.g. pathogenic or nonpathogenic) via the study drug is an SAE.

**NOTE:** The following hospitalizations are not considered SAEs:

- a visit to the emergency room or other hospital department < 24 hours, that does not result in admission (unless considered an important medical or life-threatening event)
- elective surgery, planned prior to signing consent
- admissions as per protocol for a planned medical/surgical procedure
- routine health assessment requiring admission for baseline/trending of health status
- medical/surgical admission other than to remedy ill health and planned prior to entry into the study.
- admission encountered for another life circumstance that carries no bearing on health status and requires no medical/surgical intervention (e.g., lack of housing, economic inadequacy, caregiver respite, family circumstances, administrative reason).

### **Serious Adverse Event Collection and Reporting**

- The collection of AEs will start after the signing of the informed consent. All SAEs, whether related or not related to study drug, will be collected, including those thought to be associated with protocol-specified procedures. An SAE report will be completed for any event where doubt exists regarding its seriousness.
- If the investigator believes that an SAE is not related to study drug, but is potentially related to the conditions of the study (such as withdrawal of previous therapy or a complication of a study procedure), the relationship will be specified in the narrative section of the SAE Report Form.
- SAEs, whether related or not related to study drug, and pregnancies must be reported to the IRB and sponsor within 24 hours. SAEs will be recorded on an SAE Report Form; If only limited information is initially available, follow-up reports are required. (Note: Follow-up SAE reports should include the same investigator term(s) initially reported.)
- If an ongoing SAE changes in its intensity or relationship to study drug or if new information becomes available, a follow-up SAE report will be sent within 24 hours to the Emory IRB and sponsor using the same procedure used for transmitting the initial SAE report.
- All SAEs will be followed to resolution or stabilization.

### **Non-serious Adverse Events**

- A **non-serious adverse event** is an AE not classified as serious.

- The collection of non-serious AE information should begin at initiation of study drug. Non-serious AE information will also be collected from the start of a placebo lead-in period or other observational period intended to establish a baseline status for the subjects.
- Non-serious AEs will be followed to resolution or stabilization or reported as SAEs if they become serious. Follow-up will be performed for non-serious AEs that cause interruption or discontinuation of study drug and for those present at the end of study treatment as appropriate. All identified non-serious AEs will be recorded and described on the non-serious AE page of the CRF.
- Completion of supplemental CRFs will be performed for AEs and/or laboratory abnormalities that are reported/identified during the study.

## **Overdose**

- An overdose is defined as the accidental or intentional administration of any dose of a product that is considered both excessive and medically important. All occurrences of overdose will be reported as an SAE.

## **Laboratory Test Result Abnormalities**

The following laboratory test result abnormalities will be captured on the non-serious AE CRF page or SAE Report Form as appropriate:

- Any laboratory test result that is clinically significant or meets the definition of an SAE
- Any laboratory test result abnormality that required the subject to have study drug discontinued or interrupted
- Any laboratory test result abnormality that required the subject to receive specific corrective therapy.

It is expected that wherever possible, the clinical rather than laboratory term would be used by the reporting investigator (e.g., anemia versus low hemoglobin value).

## **Pregnancy**

If, following initiation of the investigational product, it is subsequently discovered that a study subject is pregnant or may have been pregnant at the time of investigational product exposure, including during at least 6 half-lives after product administration, the investigational product will be permanently discontinued in an appropriate manner (e.g., dose tapering if necessary, for subject safety).

Protocol-required procedures for study discontinuation and follow-up will be performed on the subject unless contraindicated by pregnancy (e.g., x-ray studies). Other appropriate pregnancy follow-up procedures will be considered if indicated.

Pregnancy itself is not regarded as an AE unless there is a suspicion that the investigational product under study may have interfered with the effectiveness of a contraceptive medication.

The outcome of all pregnancies (spontaneous miscarriage, elective termination, ectopic pregnancy, normal birth or congenital abnormality) should be followed up and documented even if the patient was discontinued from the study.

The investigator will immediately notify the sponsor and IRB within 24 hours and in accordance with SAE reporting procedures. All pregnancies and outcomes of pregnancy should be reported to AstraZeneca's

designated fax line: [contact] or email: [contact] if a secure line is set up.

## **Recording of adverse events**

Adverse Events will be collected throughout the study until and including the last visit/contact.

## Variables

The following variables will be collected for each AE:

- AE (verbatim)
- The date when the AE started and stopped
- Maximum intensity
- Whether the AE is serious or not
- Investigator causality rating against the Investigational Product (yes or no)
- Action taken with regard to investigational product
- Whether this event is potentially a clinical endpoint /event of special interest
- Outcome.

In addition, the following variables will be collected for SAEs:

- Date AE met criteria for serious AE
- Date Investigator became aware of serious AE
- AE is serious due to
- Date of hospitalization
- Date of discharge
- Probable cause of death
- Date of death
- Autopsy performed
- Causality assessment in relation to Study procedure(s)
- Causality assessment in relation to Other medication
- Description of AE.
- It is important to distinguish between serious and severe AEs. An AE of severe intensity need not necessarily be considered serious. If the intensity of an AE changes, only the maximum intensity of the event will be recorded; however, the AE intensity will be recorded at the time of reporting.

Maximum intensity will be graded according to the following rating scale:

- Mild (awareness of event but easily tolerated)
- Moderate (discomfort enough to cause some interference with usual activity)
- Severe (inability to carry out usual activity)

## Causality collection

The Investigator will assess causal relationship between IP and each AE, and answer 'yes' or 'no' to the question 'Do you consider that there is a reasonable possibility that the event may have been caused by the investigational product?'

For SAEs causal relationship will also be assessed for other medication and study procedures. Note that for SAEs that could be associated with any study procedure the causal relationship is implied as 'yes'.

## Adverse Events based on examinations and tests

The results from protocol mandated laboratory tests and vital signs will be summarized in the clinical study report. Deterioration as compared to baseline in protocol-mandated laboratory values, vital signs and other safety variables will therefore only be reported as AEs if they fulfill any of the SAE criteria or are the reason for discontinuation of treatment with the investigational product.

If deterioration in a laboratory value/vital sign is associated with clinical signs and symptoms, the sign or symptom will be reported as an AE and the associated laboratory result/vital sign will be considered as additional information. Wherever possible the reporting Investigator uses the clinical, rather than the laboratory term (e.g., anemia versus low hemoglobin value). In the absence of clinical signs or symptoms, clinically relevant deteriorations in non-mandated parameters will be reported as AE(s).

Any new or aggravated clinically relevant abnormal medical finding at a physical examination as compared with the baseline assessment will be reported as an AE if they fulfill any of the SAE criteria or are the reason for discontinuation of treatment with the investigational product.

## **Hepatic disorders**

All patients with a confirmed result of AST and/or ALT  $>3$  x ULN, will have additional central laboratory tests performed throughout the study. For patients who are discontinued from the study as a result of sustained elevated liver safety abnormalities, additional central laboratory tests will be performed at the time of end of Treatment Visit.

Pre-defined liver enzyme elevations will undergo adjudication. The definitions of events to be adjudicated are provided in the Event Reporting Manual. For all events identified for adjudication, the Investigator will complete the appropriate eCRF pages and provide source documentation as detailed in the Event Reporting Manual.

## **Hematuria**

All events of hematuria (confirmed by microscopy at the central laboratory) during the study will be worked up for a possible cause. If no immediate or benign cause is identified as judged by the Investigator (e.g., menstruation, kidney stone, urinary tract infection [UTI] where hematuria is subsequently resolved after successful treatment), patients will undergo further evaluation by the investigator or another qualified professional. The choice of tests will be per local standard of care. The patient will continue to receive IP treatment during these investigations (unless otherwise contraindicated). All confirmed events of bladder cancer will lead to the discontinuation of investigational product.

## **Possible malignancies**

All possible malignancies (except for non-melanoma skin cancer) will be identified based on a pre-specified list of Medical Dictionary for Regulatory Activities (MedDRA) preferred terms. The identified events will be independently adjudicated. For all events identified for adjudication, the Investigator will complete the appropriate eCRF pages and provide source documentation as detailed in the Event Reporting Manual. The Investigator will clearly describe the event as benign or malignant if known. All confirmed events of bladder cancer will lead to the discontinuation of investigational product.

## **Renal disorders**

For patients with signs of deteriorating renal function additional monitoring needs to be conducted. Any patient with an increase  $\geq 50\%$  above baseline will be scheduled for a re-test within 1 week whenever possible.

If the re-tested serum creatinine is  $< 50\%$  above baseline the patient can resume normal visit schedule.

If the re-tested increase in increase in serum creatinine  $\geq 50\%$  above baseline, the patient's renal function will continue to be monitored according to the judgment of the Investigator. In this circumstance, the Investigator will consider evaluating the patient for potentially reversible causes of

renal dysfunction including: concurrent use of NSAIDS, antibiotics, or other medications known to affect measures of serum creatinine; volume depletion; urinary tract infection and obstructive uropathy. If the eGFR falls below 25 ml/min, continue current dose of 10mg to reduce the risk of further eGFR decline.

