## 9. Change from baseline in serum magnesium at baseline and after 12 and 26 weeks

### Safety Variables

1. All-cause mortality
2. Cardiovascular death
3. Non-fatal myocardial infarction (MI)
4. Stroke
5. Acute kidney injury (defined as doubling of serum creatinine based on the RIFLE criteria ).
6. Adverse events (AEs) and serious adverse events (SAEs). Of special interest are events including diabetic ketoacidosis (DKA), volume depletion (defined as hypotension, syncope, orthostatic hypotension or dehydration), hypoglycemic events and urinary tract infections.

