### Exclusion Criteria

1. Age  $<$  18 or  $>$  90 years.
2. Subjects with a history of type 1 diabetes.
3. Treatment with TZDs or SGLT2-i during the past 3 months of admission.
4. Recurrent episodes of severe hypoglycemia or hypoglycemic unawareness.
5. History of recurrent HF admissions considered to be due to non-compliance (evaluated by the research staff for participation)
6. Patients with clinically significant hepatic disease (cirrhosis, jaundice, end-stage liver disease, portal hypertension) and elevated ALT and AST  $>$  3 times upper limit of normal.
7. Patients with impaired renal function (GFR  $<$  25 ml/min).
9. Mental condition rendering the subject unable to understand the nature, scope, and possible consequences of the study.
10. Patients on ventricular assist devices (VADs)

11. History of heart transplant or listed for heart transplant
12. History of cardiac surgery\* (within 90 days prior to enrollment) or planned cardiac interventions\* within the following 6 months
 

\*Includes: *PCI, ablation, CRT-ICD*
13. HF due to restrictive/infiltrative cardiomyopathy, active myocarditis, constrictive pericarditis, severe stenotic valvular diseases, hypertrophic cardiomyopathy, or congenital heart disease.
14. History of SGLT2-i allergy
15. Systolic blood pressure < 100 mmHg
16. Uncontrolled hypertension, defined as a systolic blood pressure > 200 mmHg at randomization
17. Female subjects who are pregnant or breast-feeding at time of enrollment into the study.
18. Females of childbearing potential who are not using adequate contraceptive methods (as required by local law or practice).
19. In hospice or expected life expectancy less than 6 months
20. Patients with diabetic foot infection, osteomyelitis, and history of amputation of lower extremities within 6 months of admission
21. Patients anticipated to undergo major surgical procedures during the following 6 months
22. Patients with active hematuria, urinary tract infection (UTI), or history of frequent UTIs or genital mycotic infections
23. Uncontrolled atrial fibrillation or atrial flutter with a resting heart rate >110bpm documented by ECG at randomization.
24. Any condition that in the opinion of the investigator would contraindicate the assessment of 6MWD

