### **Withdrawal Criteria**

1. The subject may withdraw at will at any time.
2. The subject may be withdrawn from the trial at the discretion of the investigator due to a safety concern or if judged non-compliant with trial procedures or included in contravention to the inclusion and/or exclusion criteria.
3. Adverse events (AE), i.e., any clinical, laboratory abnormality or concurrent illness which, in the opinion of the investigator, indicates that continued participation in the study is not in the best interest of the patient.
4. Doubling of serum creatinine above the baseline value confirmed by a repeated measurement within one week (study medication can be discontinued and continue study visits as described in the premature treatment discontinuation).
5. Pregnancy or intention to become pregnant.

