**Acute kidney injury and impairment in renal function.** There have been reports of acute kidney injury in patients receiving SGLT2-I. Dapagliflozin should be avoided during prolonged fasting or fluid losses (such as gastrointestinal illness). SGLT2-i may increase serum creatinine and decreases eGFR. Patients with moderate renal impairment (eGFR less than 25 mL/min/1.73 m^2) should not be started on dapagliflozin.

**Lower limb amputation.** An increased risk for lower limb amputation (primarily of the toe) has been observed in clinical studies with SGLT2-I therapy. In the recent DECLARE study, the rate of non-traumatic lower limb amputations was not increased compared to placebo treatment. Patients at increased risk of amputations including such as a history of prior amputation and diabetic foot ulcers will not be enrolled in this trial.

**Changes in serum magnesium.** Recent reports and a meta-analysis of 18 RCTs involving 15,309 patients provided evidence that SGLT2 inhibitors significantly increase serum magnesium levels in patients with T2D. On average, serum magnesium levels were raised by 0.04-0.06 mmol/l for all SGLT2-I agents indicating a drug class effect. The mechanisms are not completely understood, but likely relates to SGLT2 i- induced glucosuria and osmotic diuresis. The significant elevations in serum magnesium levels are not known, with some studies reporting an association between high magnesium levels and total mortality in individuals with heart failure and those receiving hemodialysis. However, in the general population and in people with type 2 diabetes, high end of the normal range of serum magnesium has been associated with a lower risk of cardiovascular events, lower systolic BP by 2.00 mmHg and diastolic BP by 1.78 mmHg compared with placebo. It has been hypothesized that a modest increase in serum magnesium could have contributed to a reduction in cardiovascular mortality observed among participants with type 2 diabetes in the EMPA-REG OUTCOME trial.

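### For a patient with both a confirmed creatinine doubling and an eGFR below 25 ml/min, one renal rule allows study drug to be stopped, another says to continue it, and the protocol does not say which governs

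*Combined protocol and SAP*

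**What the plan says.** Two sections of the combined protocol and SAP bear on study drug when renal function falls.

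- **Withdrawal Criteria, item 4.** The trigger is "Doubling of serum creatinine above the baseline value confirmed by a repeated measurement within one week". The action is given in parentheses: "study medication can be discontinued and continue study visits as described in the premature treatment discontinuation". The wording permits stopping and does not require it.
- **Renal disorders.** A creatinine rise of at least 50% leads to a re-test within a week where possible. If the rise is confirmed, "the patient's renal function will continue to be monitored according to the judgment of the Investigator", and the investigator considers reversible causes. This step gives no study-drug instruction, and there is no separate step at doubling. The section then ends: "If the eGFR falls below 25 ml/min, continue current dose of 10mg to reduce the risk of further eGFR decline".

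Three other places set the context.

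- The Exclusion Criteria bar a GFR below 25 ml/min, so a patient at 25 or above can enter under that criterion.
- The acute kidney injury paragraph, under the potential risks of dapagliflozin, says patients below 25 "should not be started on dapagliflozin". That concerns starting the drug and is silent on continuing it.
- Safety Variables, item 5, uses the same creatinine threshold as the withdrawal criterion: "Acute kidney injury (defined as doubling of serum creatinine based on the RIFLE criteria".

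**The concern.** The withdrawal rule is triggered by a relative change in creatinine, the continue rule by an absolute eGFR. One patient can satisfy both on the same blood sample. A site that then stops drug under the Withdrawal Criteria departs from Renal disorders. A site that follows Renal disorders keeps study drug going in a patient who meets a listed withdrawal criterion, at the threshold the trial itself uses to define acute kidney injury. With four institutions, practice may differ according to which section is consulted.

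This is first a patient-safety matter. It also means that exposure after the event may depend on site practice, which makes later on-drug events harder to interpret.

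A smaller point is that the continue sentence names a 10 mg dose and gives a benefit of the drug as its reason. The trial is double-blind with 196 patients planned per arm, so the rule will also be applied to patients on placebo, for whom that reason cannot hold.

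**Working it through.** The plan states no figure on this point, so there is none to reproduce. The check has two parts.

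**1. What each section says about study drug**

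| Situation | Withdrawal Criteria, item 4 | Renal disorders | Result |
|---|---|---|---|
| Confirmed doubling, eGFR 25 or above | May be stopped | Monitor; nothing on study drug | No contradiction |
| eGFR below 25, no confirmed doubling | Not triggered | Continue | No contradiction |
| Confirmed doubling and eGFR below 25 | May be stopped | Continue, no exception | Unreconciled |

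**2. Can the third row occur?**

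Inputs: the entry threshold of GFR 25 ml/min (Exclusion Criteria), the doubling trigger (Withdrawal Criteria) and the continue trigger of eGFR below 25 (Renal disorders). The documents give no eGFR equation, so I assume eGFR is proportional to creatinine^(-k), with k from 1.0 to 1.2.

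- eGFR after an exact doubling = baseline × 2^(-k). This leaves 50% of baseline at k = 1.0 and 43.5% at k = 1.2.
- It falls below 25 when baseline < 25 × 2^k. This gives 25 × 2 = 50.0 at k = 1.0, 53.6 at k = 1.1 and 57.4 at k = 1.2.
- The creatinine multiple at which eGFR reaches 25 is (baseline / 25)^(1/k).

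| Baseline eGFR | After exact doubling, k = 1.0 | After exact doubling, k = 1.2 | Creatinine multiple that brings eGFR to 25 (k = 1.2 to 1.0) |
|---|---|---|---|
| 30 | 15.0 | 13.1 | 1.16 to 1.20 |
| 40 | 20.0 | 17.4 | 1.48 to 1.60 |
| 50 | 25.0 | 21.8 | 1.78 to 2.00 |
| 60 | 30.0 | 26.1 | 2.07 to 2.40 |
| 70 | 35.0 | 30.5 | 2.36 to 2.80 |

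A patient who starts at 40 and doubles creatinine ends at 17.4 to 20.0 and meets both triggers. A patient who starts at 30 crosses 25 after a rise of only 16% to 20%, and at that point meets the continue rule alone. A patient who starts at 70 and exactly doubles is still at 30.5 to 35.0 and meets the withdrawal criterion alone. The limits of 50 to 57 are for an exact doubling; a larger rise brings higher baselines into the overlap.

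**A qualification on the range.** The Hypoglycemia risk protection section says patients with chronic kidney disease beyond stage II will be excluded. That would shrink the overlap, by an amount that depends on the eGFR cut-off used for staging, which the documents do not give. It also disagrees with the threshold of 25 in the formal Exclusion Criteria, so it cannot be relied on to close the gap.

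**The case against.** The best defence is that the two rules can be read together: crossing 25 is not by itself a reason to stop, while a confirmed doubling permits stopping. The bar on starting below 25 fits that reading. Withdrawal Criteria items 2 and 3 also let the investigator withdraw a patient for a safety concern or a laboratory abnormality, so nothing forces a site to continue against its judgment.

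Much of this stands, and it rules out three stronger readings that a reader might infer.

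- **That the protocol orders a stop in one place and a continuation in another.** It does not. Item 4 permits discontinuation, and a site that continues after a doubling does not breach its literal wording.
- **That the sections conflict at every confirmed doubling.** They do not. Monitoring renal function is compatible with either stopping or continuing drug. While eGFR stays at 25 or above, Renal disorders says nothing about study drug.
- **That the renal safety comparison is confounded.** The doubling endpoint occurs before the decision to stop or continue, so that decision cannot affect whether the doubling happened. Allocation is randomized and blinded, and patients who stop are asked to continue visits.

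The defence does not remove the case where both triggers are met. Reading the rules together requires an order of precedence that the protocol never states, and the continue sentence admits no exception. Elsewhere the protocol does write such qualifiers: the Hematuria section continues treatment unless it is otherwise contraindicated, and the UTI section lets the investigator consider a temporary stop.

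**Conclusion.** The inconsistency is real and narrow. It applies to a patient who has both a confirmed creatinine doubling and an eGFR below 25. Under the assumed exponents of 1.0 to 1.2, an exact doubling produces this for baselines from 25 up to about 50 to 57. The upper limit rests on the assumed exponent and on taking the formal exclusion threshold of 25 as the operative one.

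The range shows that the overlap is possible, not how often it will occur. The documents give neither a baseline eGFR distribution nor an expected number of doublings.

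The consequence is for patient safety and for interpreting drug exposure after the event. The doubling endpoint, the sample size, alpha and the primary analysis are unaffected. No view is taken on which clinical rule is right.

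**What to change.** Reconcile Withdrawal Criteria item 4 with the Renal disorders section. Each should refer to the other, and the text should state which rule governs when a confirmed doubling and an eGFR below 25 occur together. Word the rule for blinded study medication rather than for a 10 mg dose with a drug-specific rationale. The sponsor decides the clinical content. In the same revision, reconcile the chronic kidney disease exclusion in Hypoglycemia risk protection with the Exclusion Criteria, since it determines how many patients could be affected.

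No new CRF field is essential. Investigator-prescribed stops (Treatment Compliance/Adherence), laboratory abnormalities leading to interruption or discontinuation (Laboratory Test Result Abnormalities) and the action taken with study drug for each adverse event (Variables) are already recorded. The revision should require these records for every confirmed doubling, including those after which drug is continued. This matters because the section on adverse events based on examinations and tests limits reporting of deterioration in protocol-mandated laboratory values to events that are serious or lead to discontinuation.

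The cost is wording in a few sections and a reminder to sites, with no extra visits, tests or patients.
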